---

**The following Amendment(s) and Administrative Changes are included in this revised protocol:**

Amendment No.	Date of Amendment	Local Amendment No.	Date of Local Amendment
3			
Administrative Change No.	Date of Administrative Change	Local Administrative Change No.	Date of Local Administrative Change

## PROTOCOL SYNOPSIS

---

### **A Multicenter, Double-blind, Randomized, Placebo-controlled, 4-Armed Parallel Group Study to Evaluate the Efficacy of Zolmitriptan 0.5-, 2.5- and 5-mg Nasal Spray in the Treatment of Acute Migraine Headache in Adolescents**

---

#### **International Co-ordinating Investigator**

#### **Study centre(s) and number of subjects planned**

This will be a global, multicenter study conducted in the United States (US), Latin America, and Europe. A sufficient number of male and female adolescent patients, age 12 to 17 years with an established diagnosis of migraine, will be screened to ensure that approximately 1000 patients (312 in the zolmitriptan 5 mg and placebo arms) are randomized into the study to obtain 800 evaluable patients (250, 150, 150, and 250 patients in the placebo, zolmitriptan 0.5 mg, zolmitriptan 2.5 mg, and zolmitriptan 5 mg treatment groups, respectively). Based on the results from a blinded interim analysis, the sample size could be increased to obtain a maximum of 1036 evaluable patients. Approximately 150 centers will participate in the study.

---

Study period	Phase of development
Estimated date of first patient enrolled	III
Estimated date of last patient completed	

---

#### **Objectives**

**Primary objective:** The primary objective of this study is to compare the efficacy of zolmitriptan nasal spray 0.5, 2.5, and 5 mg with placebo in the acute treatment of migraine headache in adolescents (aged 12 to 17), as measured by the primary outcome variable of pain-free status at 2 hours post treatment.

### **Secondary objectives:**

- To evaluate the efficacy of zolmitriptan nasal spray 0.5, 2.5, and 5 mg as compared with placebo in the acute treatment of migraine headache in adolescents (aged 12 to 17 years), as assessed by:
  - pain-free status
  - headache response
  - sustained headache response
  - presence and resolution of associated symptoms of photophobia, phonophobia, or nausea
  - incidence and time to use of rescue medication
  - ability to perform normal activities
  - headache recurrence
  - bilateral headache (yes/no)
  - intensity increased by movement (yes/no)
- To assess safety and tolerability of zolmitriptan when used for the acute treatment of migraine headache in adolescents.

### **Study design**

This is a global, multicenter, double-blind, randomized, placebo-controlled study with a parallel group design to evaluate the efficacy of zolmitriptan 0.5, 2.5, and 5 mg nasal spray in the acute treatment of migraine headache in adolescent patients. Patients will be randomized to treatments in the ratio of 5:3:3:5 for placebo, zolmitriptan 0.5, 2.5, and 5 mg, respectively.

### **Target subject population**

Adolescents, age 12 to 17 years with an established diagnosis of migraine, as defined by the International Headache Society (IHS) or IHS-Revised (IHS- R) criteria (see [Appendix D](#)).

### **Investigational product, dosage and mode of administration**

ZOMIG® (zolmitriptan) Nasal Spray 0.5, 2.5, and 5 mg. The nasal spray will contain 1 dose of ZOMIG®.

### **Comparator, dosage and mode of administration**

Placebo for ZOMIG® (zolmitriptan) Nasal Spray. The placebo nasal spray will contain 1 dose of ZOMIG® placebo.

## **Duration of treatment**

Eligible patients will be randomized to 1 of 4 treatment groups (zolmitriptan 0.5, 2.5, 5 mg nasal spray, or matching placebo nasal spray) to treat 1 attack of moderate or severe migraine headache during a 10-week study period after successful completion of the run-in period. When the headache pain reaches moderate to severe intensity, patients will treat it with a single dose of study drug (zolmitriptan 0.5, 2.5, 5 mg nasal spray, or matching placebo nasal spray). Headache response is defined as a reduction in migraine headache pain intensity from severe or moderate at the time of initial treatment to mild or none at a specific assessment time. If the headache pain continues at moderate or severe intensity for at least 2 hours after study drug treatment, patients will be allowed to treat it with an approved rescue medication specified by the investigator.

## **Outcome variables:**

- Efficacy

**Primary outcome variable:** pain-free status at 2 hours post treatment.

### **Secondary outcome variables:**

- Pain-free status at 15 minutes and at 1, 2, 3, 4, and 24 hours post treatment
- Headache response at 15 minutes and at 1, 2, 3, 4, and 24 hours post treatment
- Sustained headache response at 2 hours subsequent to a 1-hour headache response
- Presence of associated symptoms of photophobia, phonophobia, or nausea at 15 minutes and at 1, 2, 3, 4, and 24 hours post treatment
- Resolution of associated symptoms of photophobia, phonophobia, or nausea at 15 minutes and at 1, 2, 3, 4, and 24 hours post treatment
- Incidence and time to use of rescue medication up to 24 hours post treatment
- Ability to perform normal activities at 15 minutes and at 1, 2, 3, 4, and 24 hours post treatment
- Headache recurrence 2 to 24 hours post treatment
- Bilateral headache (yes/no) at 15 minutes and at 1, 2, 3, 4, and 24 hours post treatment
- Intensity increased by movement (yes/no) at 15 minutes and at 1, 2, 3, 4, and 24 hours post treatment

- **Safety**
  - Incidence, nature, and intensity of AEs; vital signs; physical examination changes; laboratory assessments (ie, chemistry, hematology, and urinalysis); electrocardiogram (ECG); and incidences of suicidal behavior and suicidal ideation as measured by the Columbia-Suicide Severity Rating Scale (C-SSRS).

### **Statistical methods**

Efficacy analyses will be based on the full analysis set (FAS), which will include all randomized treated patients who provide post-treatment efficacy data, classified according to randomized treatment.

Safety and tolerability assessments will be based on the safety analysis set, which will include all randomized treated patients who provide post-treatment safety data, classified according to the treatment actually received.

The primary null hypothesis to be tested is that the different doses of zolmitriptan 0.5, 2.5, and 5 mg are not different from placebo, using pain-free status at 2 hours post treatment as the primary endpoint.

The primary endpoint will be analyzed using a logistic regression model with 2-hour pain-free status as the response variable, and treatment and center as fixed factors in the model. A step-down approach is used for securing the alpha level when comparing the 3 doses of zolmitriptan against placebo for 2-hour pain-free status. Initially, zolmitriptan 5 mg is compared with placebo in terms of odds ratio. If this is significant at the 2-sided 5% level, then zolmitriptan 2.5 mg is compared with placebo and if this is significant at the 2-sided 5% level then zolmitriptan 0.5 mg is compared with placebo at the 2-sided 5% level. If the first comparison between zolmitriptan 5 mg and placebo is not significant, then the zolmitriptan 2.5 mg is not to be compared with placebo, etc. The primary analysis will be based on the FAS with the LOCF approach.

The secondary endpoints will be analyzed at the 5% significance level without multiplicity correction for descriptive purposes.

A total of 2400 patients will be enrolled to ensure 1000 randomized patients, assuming a 56% drop-out rate prior to randomization. Assuming 20% of the randomized patients drop out before treatment of a migraine headache attack, 800 patients (250, 150, 150, and 250 patients in the placebo, zolmitriptan 0.5 mg, zolmitriptan 2.5 mg, and zolmitriptan 5 mg treatment arms, respectively) will be evaluable for the primary analysis. This will provide 80% power to detect a treatment difference at the 2-sided significance level 0.05 if the true difference between zolmitriptan 5 mg treatment and placebo is 0.11 for the primary endpoint of pain-free status at 2 hours.

The power to detect a treatment difference between zolmitriptan 2.5 mg and 0.5 mg versus placebo will be 67% if the true treatment difference is 0.11. A 2-treatment, continuity-corrected, chi-square test of equal proportions is used as an approximation for the intended analysis approach in the power calculations. A difference of 0.11 in response rates is considered a clinically relevant effect. The 2-hour pain-free rate for the placebo treatment group is assumed to be the same as in a previous study (D1221C00005) conducted on zolmitriptan nasal spray in adolescent patients for both periods combined, 0.18.

Since the assumptions for the sample size calculations are uncertain, an interim analysis is planned after approximately one third of the planned patients have been treated. The sample size will be re-estimated at the interim analysis using a blinded estimation of the observed total that were 2 hours pain-free. Depending on the interim results, the sample size can increase to a maximum of 1036 total evaluable patients, requiring approximately 1295 patients to be randomized and 2943 patients to be enrolled.

The interim analysis will be performed by an independent statistician who is not involved with this trial.

	PAGE
TITLE PAGE .....	1
PROTOCOL SYNOPSIS.....	2
TABLE OF CONTENTS.....	7
LIST OF ABBREVIATIONS AND DEFINITION OF TERMS .....	12
1. INTRODUCTION .....	14
1.1 Background.....	14
1.2 Research hypothesis.....	15
1.3 Rationale for conducting this study .....	15
1.4 Benefit/risk and ethical assessment .....	15
2. STUDY OBJECTIVES.....	17
2.1 Primary objective.....	17
2.2 Secondary objectives .....	17
2.3 Safety objective.....	18
3. STUDY PLAN AND PROCEDURES .....	18
3.1 Overall study design and flow chart .....	18
3.1.1 Visit 1 (Screening/run-in period and placebo challenge) .....	20
3.1.2 Visit 2 (randomization).....	21
3.1.3 Treatment of 1 migraine attack within 10 weeks.....	22
3.1.4 Interim visit (4 weeks from randomization visit) .....	22
3.1.5 Visit 3 (final visit/end-of-study) or early termination (ET) visit.....	23
3.2 Rationale for study design, doses and control groups.....	27
4. SUBJECT SELECTION CRITERIA .....	29
4.1 Inclusion criteria .....	29
4.2 Exclusion criteria .....	30
5. STUDY CONDUCT .....	32
5.1 Restrictions during the study .....	32
5.2 Subject enrollment and randomization .....	33
5.2.1 Procedures for randomization .....	33
5.3 Procedures for handling subjects incorrectly enrolled.....	34

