The pharmacokinetics in adolescents of nasally administered zolmitriptan has been evaluated (Trial D122100004). A 5 mg dose of zolmitriptan nasal spray in both male and female adolescents has similar area under the plasma concentration curve (AUC), maximum plasma (peak) drug concentration after single-dose administration ( $C_{max}$ ), and clearance as the adult population; and therefore, similar drug exposure as in the adult population.

Dosing in adolescents is generally based on body mass index (BMI) and weight as this ensures a relatively standardized population.

The rationale for the primary objective is to demonstrate that the effect of zolmitriptan is superior to placebo after single-dose administration in the acute treatment of migraine headache in adolescents between 12 to 17 years of age. The 2-hour pain-free endpoint is the IHS recommended primary outcome in guidelines for migraine studies. This ensures migraine headache relief of appropriate duration. The endpoints for the secondary objectives are commonly used endpoints in migraine studies. Endpoints collected before and after the 2-hour timepoint are included to support the primary endpoint.

Placebo is used as the comparator since the primary objective is to evaluate the efficacy of zolmitriptan.

Baseline assessments of headache intensity and associated symptoms are included as they are needed for derivation of the endpoints.

There is no evidence of a link between triptan use and suicidal behavior. Recent research studies have noted the increased risk of suicidality in frequent adolescent migraineurs. It is important to understand if treatment affects these symptoms when present. The C-SSRS ([Posner et al 2007](#)) will be performed to assess this.

No safety monitoring committee will be required since there are no specific safety concerns. Safety will be monitored on an ongoing basis and will include AEs, vital signs, laboratory assessments, ECG, and the C-SSRS to assess suicidal risks prior to and after treatment.

An external Data Monitoring Committee (DMC) consisting of an independent statistician will perform the interim analysis for sample size re-estimation based on blinded data only. The DMC will decide on the total sample size needed for the study.

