If a randomization number is allocated incorrectly (randomized to the wrong treatment, not due to the patient not meeting the inclusion/exclusion criteria), no attempt should be made to remedy the error once study material has been dispensed. The patient will continue with the allocated number and study material. AstraZeneca or its representative should be notified as soon as the error is discovered and the error should be adequately documented. Subsequent patients will continue using the first unallocated randomization number in the original numbering sequence.

Enrollment will be monitored during randomization to ensure balanced distribution between the age groups 12 to 14 years and 15 to 17 years.

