## **6.5 Patient reported outcomes (PRO)**

### **6.5.1 Patient diary (self-assessment of headache pain, symptoms, and treatment response)**

A paper patient diary will be used for date and time stamping of patients' self-assessment of headache pain, symptoms, and treatment response.

Patients will assess migraine pain severity and rate the intensity as severe (3), moderate (2), mild (1), or none (0).

Patients will record the following data relevant to their migraine headaches:

- Headache frequency and type (run-in period only);
- Date and time headache intensity is moderate or severe prior to study treatment (baseline);
- Date and time of treatment with study drug;
- Presence of associated migraine symptoms (photophobia, phonophobia, nausea, vomiting) at baseline;
- Headache intensity prior to treatment with study drug, and at 15 minutes ( $\pm 10$  minutes) and 1 hour ( $\pm 30$  minutes), 2 hours ( $\pm 20$  minutes), 3 hours ( $\pm 30$  minutes), 4 hours ( $\pm 30$  minutes), and 24 hours ( $\pm 8$  hours) after treatment;
- Presence of associated migraine symptoms at 15 minutes ( $\pm 10$  minutes) and 1 hour ( $\pm 30$  minutes), 2 hours ( $\pm 20$  minutes), 3 hours ( $\pm 30$  minutes), 4 hours ( $\pm 30$  minutes), and 24 hours ( $\pm 8$  hours) after treatment;
- Rescue medications taken, time, and date;
- Ability to perform normal activities prior to treatment with study drug, and at 15 minutes ( $\pm 10$  minutes) and 1 hour ( $\pm 30$  minutes), 2 hours ( $\pm 20$  minutes), 3 hours ( $\pm 30$  minutes), 4 hours ( $\pm 30$  minutes), and 24 hours ( $\pm 8$  hours) post treatment;
- Headache recurrence 2 to 24 hours post treatment;
- Bilateral headache (yes/no) prior to treatment with study drug, and at 15 minutes ( $\pm 10$  minutes) and 1 hour ( $\pm 30$  minutes), 2 hours ( $\pm 20$  minutes), 3 hours ( $\pm 30$  minutes), 4 hours ( $\pm 30$  minutes), and 24 hours ( $\pm 8$  hours) post treatment;

- Intensity increased by movement (yes/no) prior to treatment with study drug, and at 15 minutes ( $\pm 10$  minutes) and 1 hour ( $\pm 30$  minutes), 2 hours ( $\pm 20$  minutes), 3 hours ( $\pm 30$  minutes), 4 hours ( $\pm 30$  minutes), and 24 hours ( $\pm 8$  hours) post treatment.

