### 12.2.2 Primary efficacy variable

The primary null hypothesis to be tested is that the different doses of zolmitriptan 0.5 mg, 2.5 mg and 5 mg are not different from placebo, using pain-free status at 2 hours post treatment as the primary variable.

The primary variable will be analyzed using a logistic regression model with 2-hour pain-free status as the response variable including treatment and center as fixed factors in the model. A step-down approach is used for maintaining the alpha level when comparing the 3 doses of zolmitriptan against placebo for 2-hour pain-free status. Initially, zolmitriptan 5 mg is compared with placebo in terms of odds ratio. If zolmitriptan 5 mg is significantly better than

placebo at the 2-sided 5% level, then zolmitriptan 2.5 mg is compared with placebo, and if it is significantly better than placebo at the 2-sided 5% level, then zolmitriptan 0.5 mg is compared with placebo. If the first comparison between zolmitriptan 5 mg and placebo is not significant, then the zolmitriptan 2.5 mg is not to be compared with placebo, etc. The primary analysis will be based on the FAS with the LOCF approach.

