### **12.2.3 Secondary efficacy variables**

The following secondary efficacy variables will be analyzed for OC and/or LOCF in the FAS:

- Pain-free status at 15 minutes and at 1, 2, 3, 4, and 24 hours post treatment;
- Headache response at 15 minutes and at 1, 2, 3, 4, and 24 hours post treatment;
- Sustained headache response at 2 hours subsequent to a 1-hour headache response;
- Presence of associated symptoms of photophobia, phonophobia, or nausea at 15 minutes and at 1, 2, 3, 4, and 24 hours post treatment;
- Resolution of associated symptoms of photophobia, phonophobia, or nausea at 15 minutes and at 1, 2, 3, 4, and 24 hours post treatment;
- Incidence and time to use of rescue medication up to 24 hours post treatment;
- Ability to perform normal activities at 15 minutes and at 1, 2, 3, 4, and 24 hours post treatment.
- Headache recurrence 2 to 24 hours post treatment;
- Bilateral headache (yes/no) at 15 minutes and at 1, 2, 3, 4, and 24 hours post treatment;
- Intensity increased by movement (yes/no) at 15 minutes and at 1, 2, 3, 4, and 24 hours post treatment.

For the binary secondary efficacy variables, the same logistic regression model as for the analysis of primary efficacy variable will be used. Time to use of rescue medication will be displayed graphically using Kaplan-Meier curves by treatment group. Comparison of treatment doses versus placebo will be based on the Cox proportional hazard model. The secondary endpoints will be analyzed at the 2-sided 5% significance level without any multiplicity correction.

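### The primary and binary secondary models omit pre-dose values that the diary already collects: a small, cheap gain in power is missed, with no bias or error in alpha or sample size

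*Protocol*

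**What the plan says.** The model is stated twice, consistently. The synopsis (Statistical methods) specifies a logistic regression with "treatment and center as fixed factors in the model". Section 12.2.2 describes the same regression, "including treatment and center as fixed factors in the model". For the binary secondary variables, Section 12.2.3 says that "the same logistic regression model as for the analysis of primary efficacy variable will be used". Time to rescue medication goes to a Cox model with no covariates named.

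Section 6.5.1 lists what patients write down before dosing. It includes "Headache intensity prior to treatment with study drug, and at 15 minutes" (and at the later times), and "Presence of associated migraine symptoms (photophobia, phonophobia, nausea, vomiting) at baseline". It also asks for pre-dose ability to perform normal activities, bilateral headache and intensity increased by movement. Section 3.2 gives the purpose of the first two items: "Baseline assessments of headache intensity and associated symptoms are included as they are needed for derivation of the endpoints". No section uses a pre-dose value as a covariate in an efficacy model.

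On age, Section 5.2.1 says "Enrollment will be monitored during randomization to ensure balanced distribution between the age groups 12 to 14 years and 15 to 17 years". Randomization is stratified by center only.

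**The concern.** Under Section 11.1.1 a patient starts at moderate or severe pain and succeeds only by reaching none at 2 hours. Starting level is therefore a plausible predictor of success, and neither the randomization nor the analysis controls it. For symptom presence, normal activities, bilateral headache and worsening by movement, the pre-dose value of the same item is an even more direct candidate.

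What is at stake is power and protection against chance imbalance. The plan has 80% power for 5 mg and 67% for the two lower doses at a difference of 0.11. Testing steps down from 5 mg, so a miss there ends the confirmatory comparisons.

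**Working it through.** **Inputs from the protocol.** Placebo rate 0.18; difference 0.11, so 0.29 on 5 mg; two-sided alpha 0.05; 250, 150, 150 and 250 evaluable patients; continuity-corrected chi-square test (Section 12.3).

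**Step 1: the plan's own figures.** Power = Φ[(d − c − 1.96·SE0)/SE1], with c = ½(1/n1 + 1/n2), SE0 from the pooled rate and SE1 from the separate rates.

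- 250 vs 250: c = 0.004, SE0 = √(0.235 × 0.765 × 2/250) = 0.0379, SE1 = √((0.1476 + 0.2059)/250) = 0.0376. Power = Φ(0.842) = 80.0%, as stated.
- 250 vs 150: c = 0.00533, SE0 = 0.0429, SE1 = 0.0443. Power = Φ(0.466) = 67.9%, against 67% stated.

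The sample size was derived without covariates and is correct on that basis. Without the continuity correction, 250 per arm gives 82.9%. That is the reference for the Wald tests below.

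**Step 2: adding severity to the primary model.** The documents give neither the share of severe attacks (s) nor the odds ratio for pain-free, severe versus moderate, so both are assumed. Each setting used 4,000 simulated trials of 250 per arm with marginal rates held at 0.18 and 0.29. Both logistic Wald tests were run on the same data, with center left out. R² is the share of outcome variance explained by severity, s(1−s)(q0−q1)²/[m(1−m)], averaged over the two arms. Here q0 and q1 are the rates in moderate and severe attacks, and m is the arm's rate.

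| Share severe | Odds ratio | R² | Power without | Power with | Change (points) | 250 × R² |
|---|---|---|---|---|---|---|
| 30% | 1.0 | 0 | 83.4% | 83.5% | +0.1 | 0 |
| 30% | 0.67 | 0.5% | 84.1% | 84.0% | −0.05 | 1.4 |
| 30% | 0.5 | 1.5% | 82.2% | 83.0% | +0.8 | 3.7 |
| 30% | 0.33 | 3.3% | 83.5% | 84.4% | +0.9 | 8.3 |
| 30% | 0.2 | 5.8% | 83.0% | 84.9% | +1.9 | 14.4 |
| 50% | 1.0 | 0 | 82.3% | 82.1% | −0.2 | 0 |
| 50% | 0.67 | 0.7% | 82.6% | 82.9% | +0.25 | 1.8 |
| 50% | 0.5 | 2.1% | 84.1% | 84.5% | +0.4 | 5.1 |
| 50% | 0.33 | 5.0% | 83.9% | 85.8% | +1.9 | 12.4 |
| 50% | 0.2 | 9.5% | 82.8% | 85.7% | +3.0 | 23.7 |

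The unadjusted column has the same true value in every row, so its spread (82.2% to 84.1%) is simulation noise. The within-row changes are paired and less noisy.

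**Step 3: where the gain comes from (50% severe, odds ratio 0.33).** The implied rates are 0.257 moderate and 0.103 severe on placebo, and 0.400 and 0.180 on 5 mg. The unadjusted log odds ratio is ln[(0.29/0.71)/(0.18/0.82)] = 0.621 with SE 0.216, so z = 2.88. The severity-adjusted log odds ratio is 0.653 with SE 0.222, so z = 2.95. Approximate power moves from Φ(2.88 − 1.96) = 82% to Φ(2.95 − 1.96) = 84%, in line with the table. The standard error does not shrink. The target moves from an odds ratio of 1.86 to a conditional one of 1.92, and z rises.

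**Step 4: chance imbalance, same setting.** The difference between arms in share severe has SD √(0.25 × 2/250) = 4.5 points. Severe and moderate attacks differ by 0.155 on placebo and 0.220 on 5 mg, on average 0.187. A one-SD imbalance therefore shifts the observed difference by 4.5 × 0.187 = 0.8 points, against a target of 11.

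**Step 5: secondary variables with their own pre-dose value.** Assume a 50% event rate. With pre-dose prevalence of 50%, R² is 2.9%, 11.1% and 22.8% at baseline odds ratios of 2, 4 and 8. With prevalence of 80% it is 1.8%, 6.5% and 12.2%.

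**The case against.** The planned model is valid, consistent between synopsis and body, and matches the center-stratified randomization. All of this stands. A reader might infer that leaving out severity biases the comparison, inflates alpha or undermines the sample size. It does none of these: randomization protects the test, and Step 1 reproduces the stated power.

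A second objection is that Section 12 defers detail to an SAP. That covers supportive analyses and the Cox covariates, which are not part of this point. It does not cover the factors of the logistic model, which the protocol itself fixes.

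Third, the gain rests on assumed inputs and could be nil. That also stands. A further four-arm simulation with 40% severe and 150 fixed centers (1,000 runs) gave +0.5, +0.9 and +1.4 points at log-odds of −0.5, −0.8 and −1.4. Center in the model does not remove the gain, but it stays small. Blinded re-estimation can also raise the total to 1036 evaluable patients, and at a true difference of 0.15 the protocol states 96% power for 5 mg. The power for 5 mg is therefore not precarious in every scenario.

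Fourth, one might say that the plan gives away precision for nothing. Step 3 shows why this is inexact: the gain is in power, and it changes the estimand.

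Fifth, monitoring of age groups might suggest that age was wrongly left out. Section 5.2.1 concerns the overall enrollment mix, not balance between arms. Section 1.1 links age to attack duration, but inclusion criterion 5 already requires a usual untreated duration of at least 3 hours. The prognostic value of age for 2-hour pain-free status is neither stated nor computed here.

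Finally, not every secondary model lacks baseline information. Symptom resolution is defined only in patients with the symptom at baseline, and the synopsis calls the secondary tests descriptive, so power there has no confirmatory weight.

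**Conclusion.** The point holds as a modest missed efficiency. The protocol fixes models that leave out pre-dose values already in the diary. For 5 mg versus placebo, adding severity is worth about 0 to +3 points of power over the assumed range. At odds ratios of 0.5 to 0.33 it is worth about +0.4 to +2 points, or roughly 4 to 12 patients per arm of 250. If severity is not prognostic, the change is within simulation noise. The omission itself is certain from the text. The size is conditional on a severe share and a prognostic strength that the documents do not give. For the four kinds of secondary variable with their own pre-dose value the gain may be larger, but those tests are descriptive. Age group is at most an optional further covariate.

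**What to change.** Before unblinding, amend the synopsis, Section 12.2.2 and Section 12.2.3 in step, and carry the change into the SAP:

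- Primary model: treatment, center and baseline headache intensity (moderate/severe) as fixed factors.
- Models for symptom presence, normal activities, bilateral headache and intensity increased by movement: add the pre-dose value of the same variable.
- Symptom resolution: add no own-baseline term, because that value is constant among the patients analyzed.

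The cost is a sentence or two of text, no new data, and one degree of freedom per two-level factor. Pain-free status is defined from a moderate or severe baseline, so the severity term should lose no patient whose primary endpoint is defined. For the secondary variables the SAP should say how a missing pre-dose value is handled. The reported odds ratio becomes conditional on baseline severity and should be labeled so, with crude rates alongside. The sample size and the blinded re-estimation rule need no change. The terms must be fixed in advance, since adding them after unblinding would look data-driven.
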